6.2.3. Analysis Methods

As few placebo patients are expected to be responders, no formal comparisons between treatment groups and placebo will be conducted for the responder and partial responder mITT populations. For the nonresponder mITT population, the following comparisons will be made for Period 1:

- for patients from originating monotherapy studies:
 - baricitinib 2 mg to baricitinib 4 mg versus baricitinib 2 mg to baricitinib 2 mg
 - baricitinib 1 mg to baricitinib 4 mg versus baricitinib 1 mg to baricitinib 2 mg
 - placebo to baricitinib 4 mg versus placebo to baricitinib 2 mg
- for patients from originating combination therapy study:
 - baricitinib 2 mg to baricitinib 4 mg versus baricitinib 2 mg to baricitinib 2 mg
 - placebo to baricitinib 4 mg versus placebo to baricitinib 2 mg

For the Period 2 substudy, the following treatment comparisons will be performed:

- for patients on baricitinib 4 mg in Period 1:
 - placebo versus baricitinib 4 mg
 - baricitinib 2 mg versus baricitinib 4 mg
- for patients on baricitinib 2 mg in Period 1:
 - placebo versus baricitinib 2 mg
 - baricitinib 1 mg versus baricitinib 2 mg

For Period 1, the main analysis method of categorical efficacy variables will use a logistic regression analysis with region, baseline disease severity from originating study (IGA 3 or IGA 4), baseline value from originating study, and treatment group in the model. For Period 2, the main analysis method of categorical efficacy variables will use a logistic regression analysis but with region, baseline disease severity at Week 52, baseline value at Week 52, and treatment

group in the model. In this case, the baseline disease severity at Week 52 can take values in 1 of 2 levels: 1) IGA of 0 or 1, and 2) IGA of 2. Firth's correction will be used in order to accommodate (potential) sparse response rates. The p-value for the odds ratio from the logistic regression model will be used for statistical inference, unless Firth's correction still results in quasi-separation. In that case, a Fisher's exact test p-value will be used for statistical inference. The difference in percentages and 100(1-alpha)% CI of the difference in percentages using the Newcombe-Wilson method without continuity correction will be reported.

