For patients treated in Period 2 but not eligible that enter the withdrawal and downtitration substudy, the censoring rule will censor efficacy data after permanent study drug discontinuation or rescue date, whichever occurs first.

Table JAHN.6.2 summarizes the various imputation techniques being used for select efficacy analyses. Sections 6.4.1 through 6.4.3 summarize the imputation methods.

Table JAHN.6.2. Imputation Techniques for Various Efficacy Variables

Population	Endpoints ^a	Imputation Method ^b
Responder and partial responder mITT Period 1	IGA(0,1), IGA(0,1,2), EASI75, 4-point Itch NRS improvement	NRI mLOCF ^c
	Exploratory endpoints	NRI (categorical endpoints) mLOCF ^c
Nonresponder mITT Period 1	IGA(0,1), IGA(0,1,2), EASI75, 4-point Itch NRS improvement	NRI mLOCF ^c
	Exploratory endpoints	NRI (categorical endpoints), MMRM (continuous endpoints) mLOCF ^c
Randomized Downtitration Withdrawal Substudy Population Period 2 nonsubstudy population Open label Period 2 non-substudy population	IGA(0,1), IGA(0,1,2), EASI75, 4-point Itch NRS improvement	NRI mLOCF ^c
	Exploratory endpoints	NRI (categorical endpoints) mLOCF ^c

Abbreviations: EASI = Eczema Area and Severity Index; IGA = Investigator's Global Assessment for atopic dermatitis; mITT = modified intent-to-treat; mLOCF = modified last observation carried forward; MMRM = mixed-model repeated measures; NRI = nonresponder imputation; NRS = Numeric Rating Scale.

^a Refer to [Table JAHN.6.6](#) and [Table JAHN.6.8](#).

^b All analysis with censoring.

^c mLOCF will be used as Primary analysis in/after Feb2021 DBL.

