6.4.3. Modified Last Observation Carried Forward

An mLOCF imputation technique replaces missing data with the most recent nonmissing postbaseline assessment. The specific modification to the LOCF is data after an intercurrent event will not be carried forward thus the mLOCF is applied after the specified censoring rule is implemented. The mLOCF assumes the effect of treatment remain the same after the event that caused missing data as it was just prior to the missing data event. Analyses using mLOCF require a nonmissing baseline and at least 1 postbaseline measure otherwise the data is missing for analyses purposes. Analyses using mLOCF help ensure the number of randomized patients who were assessed postbaseline is maximized and is reasonable for this data as data directly prior to an intercurrent event (such as initiation of rescue therapy or drop out) is likely a nonefficacious response.

mLOCF will be used as the Primary analysis in/after February 2021 DBL, as NRI may underestimate potential treatment effect in a long-term study where patients drop out for multiple reasons. For period 1 and period 2 summary and analysis, mLOCF will be used as the primary analysis for all categorical endpoints (including PROs), and NRI will be used as sensitivity analysis.

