6.11. Efficacy Analyses

The general methods used to summarize efficacy data, including the definition of baseline value for assessments are described in Section 6.2.

Efficacy analyses will generally be analyzed according to the groups in Table JAHN.6.3 and patients will be analyzed according to the IP being analyzed in the objective.

Table JAHN.6.3. Efficacy Analyses: Comparisons or Treatment Paradigms

Treatment Period	Treatment Groups: Originating Study Treatment to JAHN Treatment	Comparison or Treatment Paradigms	Analysis
Treatment Period 1 (main JAHN protocol)	Responders and Partial Responders: PBO to PBO (PBO), BARI 1 mg to BARI 1 mg (BARI 1 mg), BARI 2 mg to BARI 2 mg (BARI 2 mg), BARI 4 mg to BARI 4 mg (BARI 4 mg)	PBO, BARI 1 mg, BARI 2 mg, BARI 4 mg; descriptive	Primary, Secondary, Exploratory
	Nonresponders: PBO to BARI 2 mg, PBO to BARI 4 mg, BARI 1 mg to BARI 2 mg, BARI 1 mg to BARI 4 mg, BARI 2 mg to BARI 2 mg, BARI 2 mg to BARI 4 mg, BARI 4 mg to BARI 4 mg	PBO to BARI 4 mg vs PBO to BARI 2 mg; BARI 1 mg to BARI 4 mg vs BARI 1 mg to BARI 2 mg; BARI 2 mg to BARI 4 mg vs BARI 2 mg to BARI 2 mg	Secondary, Exploratory
Treatment Period 2 (Randomized Withdrawal and Downtitration SubStudy)	Treatment Groups: Bari 4 mg at Week 52 Bari 4 mg to Bari 2 mg Bari 4 mg to PBO Bari 2 mg at Week 52	Bari 4 mg to Bari 2 mg Bari 4 mg to PBO	Secondary

Treatment Period	Treatment Groups: Originating Study Treatment to JAHN Treatment	Comparison or Treatment Paradigms	Analysis
	Bari 2 mg to Bari 1 mg Bari 2 mg to PBO	Bari 2 mg to Bari 1 mg Bari 2 mg to PBO	
Treatment Period 2 (Non substudy) (main JAHN population)	Treatment Groups: Bari 4 mg Bari 2 mg Bari 1 mg PBO	No comparison	Secondary, Exploratory
Treatment Period 2 (Non substudy) (open label Bari 2mg population)	Treatment Groups: Bari 2mg	No comparison	Secondary, Exploratory

Abbreviations: BARI = baricitinib; PBO = placebo.

[Table JAHN.6.4](#) includes the descriptions and derivations of the primary, secondary, and exploratory efficacy outcomes.

[Table JAHN.6.5](#) provides the detailed analyses including analysis type, method and imputation, population, time point, and comparisons for efficacy analyses.

Table JAHN.6.4. Description and Derivation of Primary, Secondary, and Exploratory Efficacy Outcomes

Measure	Description	Variable	Derivation / Comment	Imputation Approach if Missing Components

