	Proportion of patients with a response of IGA 0, 1, or 2	mITT population from originating combination therapy study -non responders	Logistic regression using NRI Descriptive using mLOCF	Weeks 0-52	Secondary for IGA (0,1,2) Primary for mLOCF Sensitivity for NRI
		mITT population from open-label study	Descriptive using NRI and mLOCF	Weeks 0-52	Exploratory
		mITT population per pooled Bari 2 mg-2 mg; Bari 4 mg-4 mg	Descriptive using NRI and mLOCF	Weeks 0-52	Exploratory
		Long-term Bari 4 mg population	Descriptive using Observed, NRI and mLOCF	Weeks 52-200	Exploratory
		Randomized Downtitration Withdrawal Substudy Population	Logistic regression using NRI and mLOCF	Week 52-200	Secondary for Week 68
		Randomized Downtitration Withdrawal Substudy Population with Week 52 IGA of 0 or 1			Exploratory for Other weeks Primary for mLOCF Sensitivity for NRI
		Period 2 non-substudy population Open-label Period 2 non-substudy population	Descriptive using observed, mLOCF and NRI	Week 52 to 200	Secondary, exploratory Primary for mLOCF Sensitivity for NRI
Time to retreatment (time to IGA ≥3)	Re-Treatment Substudy Population	Descriptive	Downtitration and withdrawal period	Secondary	

Measure	Variable	Population ^a (Section 6.2.1)	Analysis Method ^b (Section 6.2.3)	Time Point	Analysis Type
	Proportion of patients with IGA ≤2 within 16 weeks after retreatment	Re-Treatment Substudy Population	Descriptive	Week 52 to 200	Secondary
Eczema Area and Severity Index (EASI) ^c	Proportion of patients achieving EASI75 (achieving EASI percent change from baseline < -75) Proportion of patients achieving EASI50 Proportion of patients achieving EASI90	mITT population from originating combination therapy study -responders, partial responders	Descriptive using NRI and mLOCF	Weeks 0-52	Secondary for EASI75 Exploratory for EASI50 and EASI90 Secondary for mLOCF
		mITT population from originating combination therapy study -non responders	Logistic regression using NRI Descriptive using mLOCF	Weeks 0-52	Sensitivity for NRI
		mITT population from open-label study	Descriptive using NRI and mLOCF	Weeks 0-52	Exploratory
		mITT population per pooled Bari 2 mg-2 mg; Bari 4 mg-4 mg	Descriptive using NRI and mLOCF	Weeks 0-52	Exploratory
		Long term Baricitinib 4 mg population	Descriptive using Observed, NRI and mLOCF	Weeks 52-200	Exploratory
		Randomized Downtitration Withdrawal Substudy Population	Logistic regression using NRI and mLOCF	Week 52-200	Secondary for Week 68 Exploratory for Other weeks

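### From the February 2021 lock, Table JAHN.6.5 conflicts with SAP Sections 6.2.3 and 6.4.3: for combination-study nonresponders it ties the 4 mg v 2 mg logistic regression to NRI, the sensitivity imputation, and leaves mLOCF, the primary one, descriptive

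*SAP*

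**What the plan says.** **Who is compared.** Under SAP Section 5.2, combination-study (JAIY) nonresponders who came from placebo or 2 mg are randomised 1:1 to 2 mg or 4 mg. All other JAIY patients keep their previous assignment. Section 6.2.3 plans two comparisons in these nonresponders: 2 to 4 mg v 2 to 2 mg, and placebo to 4 mg v placebo to 2 mg. Both serve secondary objectives in Section 4.2.

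**The model.** For Period 1, Section 6.2.3 says "the main analysis method of categorical efficacy variables will use a logistic regression analysis with region", baseline severity, baseline value and treatment as terms. Inference rests on the p-value for the odds ratio, and a Newcombe-Wilson interval for the difference in percentages is to be reported. The section ties the model to no particular imputation.

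**The imputation.** Section 6.4.3 says of Periods 1 and 2 that "mLOCF will be used as the primary analysis for all categorical endpoints (including PROs), and NRI will be used as sensitivity analysis". The footnote to Table JAHN.6.2 dates the rule: "mLOCF will be used as Primary analysis in/after Feb2021 DBL". Section 6.11.1 repeats it.

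**The table.** Section 6.11 says that Table JAHN.6.5 "provides the detailed analyses including analysis type, method and imputation, population, time point, and comparisons for efficacy analyses". For the population "mITT population from originating combination therapy study -non responders", Weeks 0-52, the method in both the IGA and the EASI responder rows is "Logistic regression using NRI Descriptive using mLOCF". The IGA label reads "Secondary for IGA (0,1,2) Primary for mLOCF Sensitivity for NRI". The substudy rows for the same endpoints instead say "Logistic regression using NRI and mLOCF".

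**The concern.** The text sets two rules: logistic regression is the main method, and mLOCF is the primary imputation. The nonresponder rows separate them. The model goes with the sensitivity imputation, and the primary imputation gets description only. A programmer who follows the table, which is the row-level specification, would produce no model-based 4 mg v 2 mg result under mLOCF.

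For combination-study patients this is the only randomised dose comparison in Period 1. A report built from the table would set mLOCF percentages beside an odds ratio and p-value computed from NRI data, which count dropouts differently. It would be unclear which result answers the secondary objective, and someone could settle that after seeing both.

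**Working it through.** The check is a comparison of passages. The plan gives no figure to reproduce.

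1. **Text rules combined.** Section 6.2.3 (logistic regression, Period 1, categorical) with Section 6.4.3 (mLOCF primary, all categorical endpoints) gives logistic regression on mLOCF data as the primary analysis and on NRI data as the sensitivity analysis.

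2. **Nonresponder rows of Table JAHN.6.5.** NRI: logistic regression, labelled sensitivity. mLOCF: descriptive. In the IGA row the label itself calls mLOCF primary. In the EASI rows the label calls it secondary, so its primary status there comes from Section 6.4.3.

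3. **Substudy rows of the same table.** Logistic regression is given for both imputations. The table therefore distinguishes the two forms, and the nonresponder entry cannot be read as shorthand for both.

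4. **Extent, from Section 4.2.** The affected secondary endpoints are IGA 0/1, IGA 0-2 and EASI75.
   - 2 mg-origin patients, Weeks 16, 36 and 52: 3 endpoints x 3 visits = 9 comparisons.
   - Placebo-origin patients, Weeks 4, 16, 24 and 52: 3 endpoints x 4 visits = 12 comparisons.
   - Total: 9 + 12 = 21.

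   The same method wording recurs for SCORAD75/90 in Table JAHN.6.5 and for the POEM and DLQI responder endpoints in Table JAHN.6.7, all exploratory. The 4-point Itch NRS endpoint at Week 16 is also secondary, but it has no combination-study nonresponder row, so this pattern does not reach it.

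5. **How far the two imputations can differ.** The documents give no dropout rate and no last-observed response rate, so these inputs are assumptions. Let d be the share of an arm that has dropped out by the visit, and r the share of those whose last usable assessment was a response. NRI counts none of them as responders and mLOCF counts d x r. Patients with no postbaseline value, whom mLOCF leaves out, are ignored here.
   - Low end: 0.10 x 0.20 = 0.02, or 2 points.
   - High end: 0.30 x 0.50 = 0.15, or 15 points.

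   This is the gap in one arm's rate. The shift in the between-dose difference is d x r in the 4 mg arm minus d x r in the 2 mg arm. It is zero if the products are equal. At opposite ends of the assumed ranges it is 0.15 - 0.02 = 0.13, or 13 points in either direction.

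**The case against.** The strongest reply is that nothing is missing. Sections 6.2.3 and 6.4.3 together already imply logistic regression on mLOCF data, with odds ratio, p-value and interval. That is right as far as it goes. A reader of the table alone might infer that the SAP plans no primary test for this comparison, and the documents do not support so broad a claim. They support a conflict between table and text. An adjusted odds ratio under NRI is planned on either reading.

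A reader might also infer an update left half done when mLOCF became primary. The substudy rows and footnote b, which still makes NRI the default for categorical endpoints, point that way. However, the IGA nonresponder row already carries the new labels. The pairing of one inferential method with descriptive mLOCF is also systematic: the continuous nonresponder rows pair MMRM on observed data with descriptive mLOCF. That fits a deliberate choice equally well, and the documents do not settle it.

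Three limits stand. Section 6.1 says that the study is not powered for such comparisons. Section 6.6 applies no multiplicity adjustment. Section 6.4.3 expects data just before an intercurrent event to show poor response, which favours the low end of the assumed range. None of them tells a programmer which instruction to follow. With p-values planned at two-sided 0.05 and no multiplicity control, it matters that the leading one is fixed in advance.

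**Conclusion.** The point holds as an internal conflict in the SAP. From the February 2021 lock, following Table JAHN.6.5 leaves 21 secondary endpoint-by-visit comparisons of 4 mg v 2 mg in combination-study nonresponders with a model-based odds ratio and p-value only under the sensitivity imputation. Following Sections 6.2.3 and 6.4.3 gives them under both.

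The word primary here describes the role of the imputation. A reader might take it to mean that the study's primary result is affected. It is not: that objective concerns responders and partial responders. Locks before February 2021 are also unaffected, because mLOCF was not yet primary. The harm is an unclear basis for inference on a secondary, unpowered comparison; no power is lost.

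The conflict rests on the text alone. The 2-15 point range rests on the assumed dropout and response shares. Any effect on the dose difference depends on dropout by arm, which the documents do not give.

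**What to change.** In the combination-study nonresponder rows of Table JAHN.6.5 (IGA, EASI, SCORAD75/90) and Table JAHN.6.7 (POEM and DLQI responder endpoints), specify logistic regression under both imputations, as the substudy rows do, with mLOCF marked primary and NRI sensitivity. Report the odds ratio, p-value and Newcombe-Wilson interval for each. Bring footnote b of both tables into line with Section 6.4.3.

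If the descriptive mLOCF entry was intended, say so, state that inference comes from NRI, and amend Sections 6.2.3 and 6.4.3 to match.

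The SAP's revision history for Version 8 says that data to Week 104, secondary endpoints included, are already locked. Date the clarification relative to the locks and label any added mLOCF test as specified after lock. The cost is table wording, one more run of existing code and a disclosed post-lock clarification.

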4.2. Secondary Objectives

The secondary objectives of this study are:

Objectives	Endpoints
Weeks 0-52	
Baricitinib Patients at Entry to Study JAHN To evaluate the effect of increasing or maintaining baricitinib dose on clinical measures and patient-reported outcomes.	
 Proportion of patients with a response of Investigator's Global Assessment (IGA) 0, 1, or 2 assessed at Weeks 16, 36, and 52 Proportion of patients with a response of IGA 0 or 1 assessed at Weeks 16, 36, and 52 (nonresponders) Proportion of patients achieving response of $\geq 75\%$ improvement from baseline in Eczema Area and Severity Index score (EASI75) from baseline of originating study assessed at Weeks 16, 36, and 52 Proportion of patients with a 4-point improvement from baseline of originating study in Itch Numeric Rating Scale (NRS) at Week 16
Placebo Nonresponders at Entry to Study JAHN To evaluate the effect of starting baricitinib 2-mg versus 4-mg on clinical measures and patient-reported outcomes.	
 Proportion of patients with a response of IGA 0, 1, or 2 assessed at Weeks 4, 16, 24, 52 Proportion of patients with a response of IGA 0 or 1 assessed at Weeks 4, 16, 24, 52 Proportion of patients achieving response of EASI75 from baseline of originating study assessed at Weeks 4, 16, 24, 52 Proportion of patients with a 4-point improvement from baseline of originating study in Itch NRS at Week 16

Objectives	Endpoints
Weeks 52-104	

All Patients Entering the Substudy To evaluate the change in clinical response after treatment withdrawal or downtitration.
 
Patients Entering the Substudy with IGA 0 or 1 To evaluate the change in clinical response after treatment withdrawal or downtitration.
	
 • Proportion of patients with a response of IGA 0, 1, or 2 assessed at 16 weeks after rerandomization (Week 68) and Week 104 • Proportion of patients with a response of IGA 0 or 1 assessed at 16 weeks after rerandomization (Week 68) and Week 104 • Proportion of patients with a response of EASI75 from baseline of originating study assessed at 16 weeks after rerandomization (Week 68) and Week 104 • Time to retreatment (time to IGA \geq3)

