
Patients Retreated during Substudy To evaluate the ability to recapture efficacy based on clinical measures after experiencing a loss of treatment benefit:
	
 • Proportion of patients with a response of IGA 0, 1, or 2 within 16 weeks of retreatment • Proportion of patients with a response of IGA 0 or 1 within 16 weeks of retreatment • Proportion of patients with a response of EASI75 from baseline of originating study within 16 weeks of retreatment

Patients Not Entered into the Substudy To evaluate the effect of maintaining baricitinib dose on clinical measures.
	
 • Proportion of patients with a response of IGA 0, 1, or 2 assessed at Week 104 • Proportion of patients with a response of IGA 0 or 1 assessed at Week 104 • Proportion of patients with a response of EASI75 from baseline of originating study assessed at Week 104

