5.2. Method of Assignment to Treatment

At entry into Study JAHN, patients who meet all criteria for enrollment will be randomized or assigned treatment by a computer-generated random sequence using an interactive web-response system (IWRS). Patients originally assigned to placebo, 1-mg baricitinib, or 2-mg baricitinib in Studies JAHL or JAHM, or patients originally assigned to placebo or 2-mg baricitinib in Study JAIY and classified as nonresponders, will be randomized in a 1:1 ratio to 2-mg baricitinib or 4-mg baricitinib and will be stratified by disease severity at baseline of JAHN (IGA 0, 1, 2 versus IGA 3 versus IGA 4). All other patients will be assigned to treatment in Study JAHN matching their prior assignment from Studies JAHL, JAHM, or JAIY.

Additional addendum patients will be permitted to enroll directly into Study JAHN on baricitinib 2 mg. These patients will not be blinded to treatment.

At Week 52, patients eligible for the withdrawal and downtitration substudy will be assigned to treatment by a computer-generated random sequence using an IWRS. Rerandomization will follow a 1:1:1 ratio allocation and will be stratified by disease severity (IGA 0, 1 versus IGA 2). Patients entering the substudy on baricitinib 4 mg will be rerandomized to baricitinib 4 mg, baricitinib 2 mg, and placebo; patients entering the substudy on baricitinib 2 mg will be rerandomized to baricitinib 2 mg, baricitinib 1 mg, and placebo.

The IWRS will be used to assign blister packs, each containing double-blind IP tablets, to each patient, starting at Visit 1 (Week 0), and at each visit up to and including Visit 21 (Week 184). Site personnel will confirm that they have located the correct blister packs by entering a confirmation number found on the blister packs into the IWRS.

This study will be conducted internationally in multiple sites. [Table JAHN.5.1](#) describes how regions were defined for stratification in the originating studies.

Table JAHN.5.1. Geographic Regions for Stratification

Region	Country
Europe	Austria, Czech Republic, Denmark, France, Germany, Hungary, Italy, Poland, Spain, Switzerland
Japan	Japan
Rest of World	Argentina, Australia, India, Israel, Korea, Mexico, Russia, Taiwan

6. A Priori Statistical Methods

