For the DBL in December 2021 and final DBL, the following analysis populations are defined for efficacy and health outcome analyses.

Randomized Downtitration Withdrawal Substudy Population: All patients (including open-label patients) who are rerandomized at Week 52, enter the substudy, and receive at least 1 dose of the IP in Period 2.

Re-Treatment Substudy Population: A subset of Randomized Downtitration Withdrawal Substudy Population who experience IGA ≥ 3 at any time in Period 2 and receive at least 1 dose of retreatment of the original dose.

Period 2 Nonsubstudy Population: All patients randomized at Week 0 of main Study JAHN (excluding open-label patients) who are not eligible to enter the substudy at Week 52 and receive at least 1 dose of the IP in Period 2.

Open-Label Period 2 Nonsubstudy Population: All patients enrolled in the open-label addendum who are not eligible to enter the substudy at Week 52 and receive at least 1 dose of the IP in Period 2.

Long-Term Baricitinib 4 mg Population: Patients initially randomized to baricitinib 4 mg in the originating studies and remain on 4-mg up to Week 52 of Study JAHN. At Week 52 of Study JAHN, patients also need to continue 4-mg and receive at least one dose in Period 2 regardless of eligibility of entering sub-study.

Safety population: For the purpose of Study JAHN alone, the safety population is defined as all patients who received at least 1 dose of IP in Study JAHN and who did not discontinue from the study for the reason ‘Lost to Follow-up’ at the first postbaseline visit in Study JAHN. For the safety analysis of Treatment Period 2, patients with at least 1 dose of IP in Treatment Period 2 will be included in the safety analysis of Treatment Period 2.

Safety analyses will be performed using the safety population and will be analyzed according to the following treatment groups (or cohorts) defined in [Table JAHN.6.1](#). Patients will be analyzed according to the dosing regimen to which they were assigned.

Table JAHN.6.1. Safety Population Treatment Groups

Treatment Groups for Treatment Period 1 (Week 0-52)	Definition
PBO	Placebo at entry to Study JAHN followed to end of Treatment Period 1 or censored at treatment change
BARI 1 mg	BARI 1 mg followed to end of Treatment Period 1 or censored at dose or treatment change
PBO/BARI 1 mg to BARI 2 mg	PBO/BARI 1 mg switching to BARI 2 mg at entry to Study JAHN followed to end of Treatment Period 1 or censored at dose or treatment change

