Validated Investigator's Global Assessment for AD (IGA)	The validated IGA of the patient's overall severity of their AD, based on a static, numeric 5-point scale from 0 (clear) to 4 (severe). The score is based on an overall assessment of the degree of erythema, papulation/induration, oozing/crusting, and lichenification.	IGA score	Single item. Range: 0-4 0 represents "clear" 4 represents "severe"	Single item, missing if missing.
		
 ▪ IGA (0,1) ▪ IGA (0,1,2) 	
 ▪ Observed score of 0 or 1 ▪ Observed score of 0, 1, or 2 	Single item, missing if missing.
		Relapse	If IGA score at any visit after Week 52 is observed to be >2 then relapse = 'Y'	Missing if all post-Week 52 IGA assessments are missing
Eczema Area and Severity Index (EASI)	The EASI assesses objective physician estimates of 2 dimensions of atopic dermatitis – disease extent and clinical signs (Hanifin et al. 2001) – by scoring the extent of disease (percentage of skin affected: 0 = 0%; 1 = 1-9%; 2 = 10-29%; 3 = 30-49%; 4 = 50-69%; 5 = 70-89%; 6 = 90-100%) and the severity of 4 clinical signs (erythema, edema/papulation, excoriation, and lichenification) each on a scale of 0-3 (0 = none, absent; 1 = mild; 2 = moderate; 3 = severe) at 4 body sites (head and neck, trunk, upper limbs, and lower limbs). Half scores are allowed. Each body site will have a score that ranges from 0-72, and the final EASI score will be obtained by weight-averaging these 4 scores. Hence, the final EASI score will range from 0-72 for each time point.	EASI score	Derive EASI region score for each of head and neck, trunk, upper limbs, and lower limbs as follows: EASI _{region} = (Erythema + edema/papulation + Excoriation + Lichenification) * (value from percentage involvement), where erythema, edema/papulation, excoriation, and lichenification are evaluated on a scale of 0-3 and value from percentage involvement is on a scale of 0-6. Then total EASI score is as follows: EASI = 0.1*EASI _{head and neck} + 0.3*EASI _{trunk} + 0.2*EASI _{upper limbs} + 0.4*EASI _{lower limbs}	N/A – partial assessments cannot be saved
		
 ▪ Change from baseline in EASI score ▪ Percent change from baseline in EASI score 	Change from baseline: observed EASI score – baseline EASI score % change from baseline: $100 \times \frac{\text{Observed score} - \text{Baseline}}{\text{Baseline}}$	Missing if baseline or observed value is missing.

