6.11.2. Secondary and Exploratory Efficacy Analyses

There will be no adjustment for multiple comparisons for any analyses. The secondary and exploratory efficacy analyses are detailed in Table JAHN.6.4. Health outcomes analyses are described in Section 6.12.

For patients entering the downtitration and withdrawal substudy who need to be retreated, a summary of treatment responses containing proportion of patients with IGA (0, 1, 2), IGA (0, 1), and EASI75 response will be provided. A summary of the time to retreatment will also be provided.

Note that the exploratory efficacy analyses on a continuous outcome that is measured over time use a slightly different estimand which is to estimate the effect of long-term therapy with baricitinib on a specific endpoint evaluated at specified time points using the mITT population assuming all patients remained in their treatment throughout the defined period of the study.

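### Time to retreatment is an endpoint for everyone entering the withdrawal substudy, but Table JAHN.6.5 summarises it only in patients who were retreated

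*SAP*

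**What the plan says.** SAP Section 4.2 puts time to retreatment among the Weeks 52-104 secondary endpoints. Its first objective group reads "All Patients Entering the Substudy To evaluate the change in clinical response after treatment withdrawal or downtitration", and the second is the subset entering with IGA 0 or 1. Retreated patients have their own objective: "Patients Retreated during Substudy To evaluate the ability to recapture efficacy based on clinical measures after experiencing a loss of treatment benefit". The endpoints under that objective are responses within 16 weeks of retreatment; time to retreatment is not among them.

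Table JAHN.6.5 has one row for the endpoint, "Time to retreatment (time to IGA" at or above 3). The population is the Re-Treatment Substudy Population, the method is descriptive and the type is secondary. Section 6.2.1 defines that population as the part of the substudy population with IGA of 3 or more "at any time in Period 2 and receive at least 1 dose of retreatment of the original dose".

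The same table analyses the IGA and EASI response proportions in the full rerandomised population and in the "Randomized Downtitration Withdrawal Substudy Population with Week 52 IGA of 0 or 1".

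Section 6.11.2, after a sentence on patients who need retreatment, adds only: "A summary of the time to retreatment will also be provided". It names no wider population, no estimator and no censoring.

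**The concern.** The population is selected on the outcome. A patient enters the summary only after losing response and being redosed, so every analysed patient has the event and none can be censored. Patients who hold their response to the end of follow-up, who are the main evidence on whether a lower dose or withdrawal is tolerated, drop out of the endpoint meant to describe them. Patients who reach IGA of 3 or more without a retreatment dose are also lost, although the endpoint is labelled as time to that IGA score.

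Two things follow. Within an arm, the summary understates the time to loss of response whenever some patients keep it. Between arms, each arm loses a different share of its patients for a reason that depends on the outcome, so the balance from rerandomisation ("Rerandomization will follow a 1:1:1 ratio allocation and will be stratified by disease severity") no longer holds. No other row fills the gap. Table JAHN.6.4 defines a Relapse variable ("If IGA score at any visit after Week 52 is observed to be" above 2), but Table JAHN.6.5 gives it no analysis row.

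**Working it through.** **No figure to reproduce.** The documents give no event count, median or hazard ratio for this endpoint. The mismatch follows from setting SAP Section 4.2 (all entrants) beside Section 6.2.1 and Table JAHN.6.5 (retreated patients only). The arithmetic below only illustrates its size.

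**Inputs from the SAP.**
- About 600 substudy entrants (Section 6.1).
- Two entry doses, each rerandomised 1:1:1 (Section 5.2), so six arms averaging 600/6 = 100 patients. The split by entry dose is not given.
- Follow-up F = 52 weeks, from the Weeks 52-104 objective. Period 2 runs to Week 200, so 200 - 52 = 148 weeks is shown as well.

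**Assumed.** The fraction retreated, the shape of the event times, and no dropout. Each pair contrasts a continued-dose arm with a placebo arm.

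**Formulas (exponential, fraction p retreated by T weeks).**
- Rate λ = -ln(1-p)/T; fraction retreated by the end of follow-up q = 1 - exp(-λF); excluded = 1 - q.
- Retreated-only median = -ln(1 - q/2)/λ; all-patient median = ln 2/λ, called not reached if beyond F.
- Mean retreatment-free time to F in all patients = q/λ; mean time in retreated patients = 1/λ - F(1-q)/q.

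**Main case, 20% v 60% by 52 weeks.**
- λ = -ln(0.8)/52 = 0.00429 and -ln(0.4)/52 = 0.01762; hazard ratio ln(0.4)/ln(0.8) = 4.1.
- Retreated-only medians: -ln(0.9)/0.00429 = 24.6 and -ln(0.7)/0.01762 = 20.2 weeks.
- All-patient medians: 161.5 (not reached) and 39.3 weeks.
- Mean retreatment-free time over 52 weeks, all patients: 46.6 v 34.1 weeks. Mean time, retreated only: 25.0 v 22.1 weeks.
- Excluded: 80% v 40%, about 80 v 40 patients at 100 per arm.

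**Range (medians in weeks).**

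| Assumed retreated | Follow-up | Retreated-only median | All-patient median | Excluded |
|---|---|---|---|---|
| 20% v 60% by 52 weeks | 52 | 24.6 v 20.2 | not reached v 39.3 | 80% v 40% |
| 10% v 50% by 52 weeks | 52 | 25.3 v 21.6 | not reached v 52.0 | 90% v 50% |
| 40% v 80% by 52 weeks | 52 | 22.7 v 16.5 | not reached v 22.4 | 60% v 20% |
| 20% v 60% by 16 weeks | 52 | 21.4 v 11.2 | 49.7 v 12.1 | 48% v 5% |
| 20% v 60% by 52 weeks | 148 | 62.4 v 35.3 | not reached v 39.3 | 53% v 7% |

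In the last two rows nearly all of the second arm is retreated, and its median is little changed.

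**Direction between arms.** Take Weibull times S(t) = exp(-(t/s)^k), s = T/(-ln(1-p))^(1/k), with 20% v 60% by T = F = 52. The retreated-only median solves 1 - S(t) = (1 - S(52))/2. Shapes k = 0.5 v 1 give 11.6 v 20.2 weeks, so the arm that loses response less often looks worse. Shapes 2 v 0.5 give 35.7 v 7.9. The retreated-only contrast can therefore shrink, widen or reverse.

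**The case against.** The strongest reply is that the full-population information is already planned. The study-design notes say retreatment is automatic at IGA of 3 or more, which is exactly failure of IGA 0, 1 or 2. Efficacy data after retreatment are censored (Section 6.4). Nonresponder imputation then scores later visits as failures, and modified LOCF carries the triggering score forward. The IGA 0, 1 or 2 rows, analysed between arms by logistic regression in all rerandomised patients and in the IGA 0 or 1 subset, thus come close to a visit-by-visit retreatment-free proportion. This stands and limits the harm. It does not supply time to retreatment, and it scores dropouts as failures or carries their last value forward instead of censoring them.

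The row is also descriptive, with no contrast specified and no multiplicity control (Section 6.6). That is true, but a descriptive summary must still describe the group in its objective. Time to retreatment among retreated patients is a legitimate description; it does not answer the Section 4.2 question.

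The 52-week window is one choice. With 148 weeks the exclusions fall to 53% v 7%, and site roll-off (Section 3, Version 8) would place actual follow-up in between. That is why both are shown.

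How retreatment applies in the continued-dose arms is unclear from these documents: Table JAHN.6.1 has no censoring at retreatment for them. This makes the size in those arms less certain, not the mismatch. Patients who reach the IGA threshold but are not redosed should be few if retreatment is automatic.

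**Conclusion.** The concern holds. Followed as written, Table JAHN.6.5 yields a summary selected on the outcome, which cannot answer the Section 4.2 objective. The population mismatch rests on the text alone and needs no assumption. Its size does: across the exponential scenarios, between 5% and 90% of an arm is excluded. In the main case a hazard ratio of 4.1 appears as a gap of about 4 weeks (24.6 - 20.2 = 4.4) between medians. An arm in which nearly everyone is retreated is hardly affected, and the direction of the distortion between arms is not fixed. The damage is confined to one descriptive secondary endpoint. It should be fixed, but it does not threaten the primary analysis or the response proportions.

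**What to change.** In Table JAHN.6.5, assign time to retreatment (time to IGA of 3 or more) to the Randomized Downtitration Withdrawal Substudy Population and to its Week 52 IGA 0 or 1 subset, by rerandomised arm. Then:

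- Give Kaplan-Meier or cumulative-incidence estimates from the first Period 2 dose. Section 6.2.3 already uses cumulative incidence functions for time to first response.
- Censor patients without the event at their last assessment, and state whether study-drug discontinuation is censored or treated as a competing event.
- Where the median is not reached, report the proportion retreated by Week 68 and by Week 104, or the restricted mean.
- Keep the Re-Treatment Substudy Population for the recapture endpoints. Add a sentence in Section 6.4 that the retreatment part of the Period 2 censoring rule does not apply to them, since their data arise after retreatment.
- Label the change as a correction of the population, because Section 3 states that data to Week 104 are already locked.

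The cost is one table-row edit, one clarifying sentence and a standard time-to-event display. No new data are needed.
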